**Hiprex (methenamine hippurate) is one of the most widely prescribed antiseptics for the prophylaxis of RUTIs**[cit]. Earliest recorded usage of methenamine as a urinary antiseptic was described in 1899. Methenamine is hydrolyzed to ammonia and formaldehyde, which is bacteriostatic or bactericidal depending on its concentration. The rate of this hydrolysis was found to be greater in solutions with lower pHs, achieving formaldehyde concentrations of clinical use at prescription dosage when the pH was less than 6.0. Although the urine pH range varies from 5 to 8, a recent study from our group in post-menopausal women identified an average urine pH around 6.0 with daily variability in several patients, possibly related to diet intake. Furthermore, as methenamine is hydrolyzed, the production of ammonia alkalinizes the solution, slowing down the reaction. Thus, in 1961, in order to increase efficacy, its formulation with adding hippurate, which increases the acidity of urine, as Hiprex, was developed.

**A literature review on the metabolism and urinary excretion of methenamine produced sparse results.** Studies by Gollamudi and Strom detailed the use of silica cartridges to determine the concentration of methenamine and formaldehyde in a solution and test this new method on human urine after administration of Hiprex to subjects. However, this work has limitations, since only 11 participants were tested and the urine samples were only taken after the first dose of Hiprex rather than after several days or months of Hiprex intake. Strom also analyzed the kinetics of methenamine, finding that a methenamine concentration of 750 µg/mL at pH 6.0 could produce bactericidal concentrations of formaldehyde after 3 hr and that the hydrolysis of methenamine occurred 20 times faster at a pH of 5.0 versus 6.0^14. Another study determined that the concentration of formaldehyde in urine adequate to produce a bacteriostatic effect (25 µg/mL) could be attained by adding 0.6 mg/mL of methenamine to urine at a pH ≤ 5.7 or 1 mg/mL at pH ≤ 5.85. Because the two latter experiments produced their results *ex vivo*, the rate of excretion of methenamine into the urine and the proof of its metabolism of conversion to formaldehyde in a patient's urine after an oral intake of 1 gm twice a day as currently recommended remains untested.

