### 3. Concise Summary of Project:

#### Study Design:

[figure not shown]
There will be two parts to this project. Part 1 will be a prospective assessment of the urinary effects of Hiprex in women with RUTIs, such as acidity and concentration of formaldehyde, to determine the best oral concentration to inhibit bacterial growth in urine for each enrolled patient. Part 2 will be a long-term assessment of Hiprex on RUTI evolution in women with a longstanding history of RUTIs, with Hiprex taken at a proper dosing (as established in Part 1) and with regular urine checks at subsequent visits up to one year of follow-up.

Part 1: Women between age 50 and 85 presenting to the outpatient UTSW Urology clinic who are currently taking Hiprex (or any methenamine-containing product) or are willing to be started on Hiprex and do not meet exclusion criteria (see below) will be invited to participate in the study. During their first study visit (V1), they will be consented for this long-term prospective study. The documentation of RUTI based on the current definition of 3 documented and treated UTIs in the past year or 2 in the past 6 months will be recorded. A 3 day diary with recordings of urine pH before each meal and before bed will be obtained to document that the patient has consistent low urine pH (<6), a critical condition for methenamine conversion to formaldehyde. Then the patient will be asked to take a tablet of Hiprex 1gm and to provide one subsequent urine samples at 1 hour after the intake of Hiprex. These midstream urine samples will be processed and transferred to our Lab on campus (K2 building) before being sent to our partnering lab at UTD run by [name] for testing, including urine pH testing, and the measurements of methenamine and aldehyde produced in these urine samples.

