#### Outcome variables and endpoints:

##### Primary outcome:

To confirm that the use of Hiprex will decrease the recurrence of symptomatic UTIs, our primary outcome will be the number of UTI events (namely UTI symptoms with positive urine cultures, or UTI-like episodes requiring antibiotic treatment) during the 1 year of the study period.

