#### Follow-up:

Patients will be asked to return to clinic for 3 follow-up visits at: 3 months (V1), 6 months (V2), and 12 months (V3) after starting Hiprex. This research visit timing corresponds to standard-of-care clinic visits include those at 3 months, 6 months, and 12 months.

At each of these visits, patients will be asked to withhold their first dose of Hiprex until they arrive to clinic. Urine samples will be collected at baseline, then 1 hours after the dose intake. These samples will be tested according to the same protocol in the lab of [name]. In addition, patients will be administered a UTI Symptom Assessment (UTISA) questionnaire and queried about any UTI symptoms and Hiprex-associated symptoms since their last visit. If the concentration of methenamine/formaldehyde in the urine sample is found to be inadequate for bacteriostatic or bactericidal activity, the dosage might be increased to 1.5 PO BID, and/or diet-adjustment might be considered to decrease urine pH if found to be not sufficiently acidic. For patients unable to reach appropriate low pH urinary levels after the above modifications, they will be removed from the study and will not continue with the longitudinal portion.

Data:

The dataset will be extracted from EPIC and will include demographic data (age, gender, race, height, weight) as well as culture data from prior urinary tract infections, comorbid conditions (i.e. diabetes, renal insufficiency, etc.), hormonal status, methenamine usage history, and urological history (including possible surgical interventions). See Excel document.

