## **6. Criteria for Inclusion of Subjects:**

- a. Female
- b. Age 50 – 85
- c. Have RUTIs (at least 2 UTIs within the past 6 months or 3 within the past year)

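### Women who cannot reach a low urine pH are removed after starting Hiprex, and the primary outcome is a one-year count without person-time, so the UTI rate may look too low.

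*Combined protocol and SAP*

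**What the plan says.** The combined protocol and SAP deals with urine pH and the primary outcome in five places.

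- **Section 4, Follow-up.** Visits are at "3 months (V1), 6 months (V2), and 12 months (V3) after starting Hiprex". If urinary drug levels or acidity are inadequate, the dose or diet may be changed. The removal rule follows: "For patients unable to reach appropriate low pH urinary levels after the above modifications, they will be removed from the study". The same sentence ends their part in the longitudinal follow-up.
- **Section 3, Primary outcome.** The text reads "our primary outcome will be the number of UTI events", counted "during the 1 year of the study period". No rate, denominator or exposure adjustment is given.
- **Section 3, Study Design, Part 1.** A three-day diary at the first visit is meant "to document that the patient has consistent low urine pH (<6", which the protocol calls critical for conversion to formaldehyde.
- **Section 6, Inclusion.** The criteria are sex, age and UTI history ("Have RUTIs (at least 2 UTIs within the past 6 months or 3 within the past year"). There is no pH criterion.
- **Section 14, Biostatistics.** This gives the goal of 100 patients and says that the data will inform power calculations for a randomised trial. It names no analysis set and does not say how removed women are handled.

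**The concern.** Removal depends on a measurement taken after treatment has begun. On the protocol's own premise, the women removed are those in whom the drug should work least. There is no control arm to share the selection.

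Two separate problems follow. The first is selection: UTIs that removed women have later in the year are never observed. The second is lost time: a woman removed part-way has less than a year in which to have events, and a plain count does not show this.

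Both push the observed UTI burden down. A Hiprex rate that is too low would overstate the effect assumed against placebo in the later trial and leave that trial too small. The outcomes of women who cannot acidify their urine, which that trial would also need for planning, would be known only up to removal.

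**Working it through.** The plan has no figure to reproduce, because the 100 patients are given without an event rate, effect size or dropout allowance. The check is an expected-value calculation.

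**Timing (from the documents).** Removal comes only after modifications, and these are prompted by follow-up results. The scheduled visits are months 3, 6 and 12. A woman first found inadequate at month 3 can be rechecked at a scheduled visit no earlier than month 6. If she is first found inadequate at month 6, the next scheduled check is month 12, and no time is lost. The illustration therefore uses removal at month 6, so t = 6/12 = 0.5.

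**Assumptions (not in the documents).**
- r = 1.2 UTIs per year in women who reach low pH. It cancels from every percentage below.
- f = 0.30 removed; range 0.10 to 0.50.
- k = ratio of the UTI rate in removed women to the rate in the others; 1 to 2.

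**Formulas.**
- True mean, all women who start: (1−f)r + f·k·r
- Raw count per woman, partial years treated as full: (1−f)r + f·k·r·t
- Completers only: r
- Person-time rate: raw count ÷ [(1−f) + f·t]

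**Doubled rate (k = 2), f = 0.30.**
- True: 0.84 + 0.72 = 1.56
- Raw: 0.84 + 0.36 = 1.20, which is 23% low
- Completers: 1.20, also 23% low (equal to the raw count only because k·t = 1)
- Person-time: 1.20 ÷ 0.85 = 1.41, which is 9.5% low

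**Equal rates (k = 1), f = 0.30.**
- True: 1.20
- Raw: 0.84 + 0.18 = 1.02, which is 15% low
- Completers: 1.20, unbiased
- Person-time: 1.02 ÷ 0.85 = 1.20, unbiased

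**Range for the raw count at month 6.** The shortfall is f·k·0.5 ÷ [(1−f) + f·k].

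| Removed | k = 1 | k = 2 |
|---|---|---|
| 10% | 5% | 9% |
| 30% | 15% | 23% |
| 50% | 25% | 33% |

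A follow-up offset alone corrects the lost time but not the selection. If every woman is followed to month 12, the expected mean equals the true value by construction.

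**The case against.** The strongest defence is that the selection is partly intended. Section 1 evaluates benefit once formaldehyde is confirmed at a suitable acid pH, and the Recruitment text in section 3 refers to efficacy in the right pH conditions. For that narrower question, some restriction is legitimate. However, the Primary outcome text states no such restriction, membership is settled by results obtained during treatment, and the lost follow-up time remains.

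It can also be said that the first-visit diary may screen out women likely to fail. It may reduce removals, but the Follow-up rule shows that some are still expected, and section 6 does not make the diary result a condition of entry.

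That this is a pilot without a hypothesis test limits the consequences, but planning input for a trial is its stated product.

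A reader might infer three stronger points that the documents do not support:

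- **That women leave at month 3.** No scheduled recheck after modification falls before month 6.
- **That failure will be common.** Section 2 reports that a study in post-menopausal women "identified an average urine pH around 6.0 with daily variability in several patients", but does not say that they were taking Hiprex, and the same section says that hippurate acidifies urine. The removal rule uses follow-up values after modification and not the entry diary, so the diary gives no estimate of the share removed.
- **That removed women's earlier events are discarded, or partial counts treated as full years.** The documents do not say. The share failing on pH is also not lost, since it can be counted from the removals.

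**Conclusion.** The point stands in a limited form. As written, the plan ends follow-up on the basis of a post-treatment pH result and pairs this with a one-year count that has no person-time. Nothing in section 14 offsets either.

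The UTI rate among women who start Hiprex will be understated if removed women have more UTIs. This rests on the protocol's own premise about acid urine, which is untested here. If rates are equal, only a raw count that treats partial years as full is biased.

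The illustrative shortfall is 23% for the raw count, and 5% to 33% over the range examined. These figures show direction and plausible scale under assumed inputs; they do not predict what the study will find.

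**What to change.** 1. **Follow-up.** Whatever is decided about treatment, continue collecting UTI outcomes to month 12 through the existing standard-of-care visits and EPIC. The current extraction list covers prior infections, so add on-study UTI events and antibiotic-treated episodes.
2. **Primary analysis.** Include all enrolled women who take Hiprex on study and report UTIs per person-year, for example by negative binomial regression with log follow-up time as offset. Start the clock at the first on-study dose, or at enrolment for women already on methenamine.
3. **Acid-urine question.** Report women who reach low pH as a secondary subset, classified at one landmark visit named in advance and counting only later events. Month 3 leaves nine months of events but precedes any scheduled recheck after modification; month 6 allows a recheck but leaves six months. Also report the share not reaching low pH.
4. **Wording.** Reconcile the pH statements in Study Design (Part 1), Follow-up and section 6. Which clinical rule applies is for the investigators to decide.

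The cost is an amendment, some additional data collection and probably a less favourable headline rate.

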## **5. Sub-Study Procedures:**

None.

## **6. Criteria for Inclusion of Subjects:**

- a. Female
- b. Age 50 – 85
- c. Have RUTIs (at least 2 UTIs within the past 6 months or 3 within the past year)

## **7. Criteria for Exclusion of Subjects:**

- a. Being on antibiotics at baseline (i.e. suppressive therapy or antibiotic therapy for urinary or non-urinary infections)
- b. Neurogenic bladder condition
- c. Using urinary catheters (including Foley catheter, intermittent catheterization, and suprapubic catheter)
- d. Uncontrolled diabetes (HbA1c > 9)
- e. Chronic renal failure defined as serum creatinine > 1.5 mg/dL
- f. History of liver disease
- g. Patients from out of town, in whom follow-up will not be possible
- h. Pregnancy
- i. Allergy to Hiprex
- j. Inability to take Hiprex reliably at home, such as having psychosis, dementia, or swallowing disorders
- k. Non-English speakers

## **8. Sources of Research Material:**

Information from medical records will be included in a de-identified fashion. Confidential information will initially be recorded to facilitate returning to the medical record if needed for more information until the end of the study, at which time the confidential information will be destroyed.

## **9. Recruitment Methods and Consenting Process:**

Once a potential patient is identified, consent will be obtained in the office. All data will be de-identified for analysis. An information sheet will be provided to all subjects.

## **10. Potential Risks:**

- a. To the participants who were already taking Hiprex, there are no direct risks because this study would not change their routines.
- b. To the participants who were not initially taking Hiprex, risks include any adverse side effects associated with the medication; however, patients will be monitored very closely after the start on Hiprex therapy.
- c. Tracked information will be used from patient records (EMR in EPIC), and identifiable information will be removed prior to analysis to ensure anonymity. Thus, all possible efforts will be made to protect patient confidentiality. Potential breach of PHI will be minimized with use of encrypted data devices stored in locked and protected areas.

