In summary, RUTIs can be debilitating in a large proportion of women. Despite the popularity of Hiprex as an RUTI prophylactic agent, there are still **large gaps of knowledge** regarding its use. Among them are its *in vivo* metabolism, including the measurements of urinary excretion of both methenamine and formaldehyde, the optimization of urine pH under 6.0 to enhance Hiprex presumed mechanism of action, and on the clinical side, the effectiveness and safety of Hiprex in geriatric patients as well as those with comorbidities, along with its cost-effectiveness over other long-term prophylactic agents for RUTI management.

Table 1: Literature review on the effect of Hiprex (HX) in women

Author and Year	Study Design	Number of Subjects	Indication	Hiprex dose	Outcome Measures	Findings
Furness 1975 	RCT	226	Pregnant with asymptomatic bacteriuria	1 g BID for ≥7 days vs methenamine mandelate 1 g QID vs no treatment	Symptomatic UTI, adverse events	
 
No significant difference in symptomatic UTI
 
No relevant adverse events
 

Gundersen 1986 	RCT	50	Post-menopausal	1 g BID for 6 months vs placebo	Symptomatic UTI, bacteriuria, adverse events	
 
Decrease in symptomatic UTI with HX
 
Side-effects of nausea and rash
 

Hoivik 1984 	RCT	52	Pre-menopausal	1 g QD or BID vs placebo (duration of treatment unknown)	Symptomatic UTI, adverse events	
 
Decrease in symptomatic UTI with HX
 
Side-effect of bladder stinging
 

Knoff 1985 	RCT	64	After gynecological operations requiring short-	2 g BID for 7 days vs placebo	Symptomatic UTI, bacteriuria, adverse events	
 
Decrease in symptomatic UTI with HX (3.2% of HX vs
 

			term catheterization			27.6% of placebo) 
 
Decrease in bacteriuria with HX (3.2% of HX vs 41.4% of placebo)
 
Side-effects of sore throat
 

Ladehoff 1984 	RCT	300	After gynecological operations requiring short-term catheterization	500 mg BID for 8-13 days vs no treatment	Bacteriuria, adverse events	
 
Decrease in bacteriuria with HX (30.3% of HX vs 45.6% of no treatment)
 
Side-effect of nausea
 

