#### Part 2:

Patients already on a methenamine drug will be queried on the history of their exposure (duration of intake, effect on RUTI, current urine pHs, etc). Patients will provide a urine sample. If the urine culture is negative, the patient will begin their prescription of Hiprex by manufacturer recommendations (if not already doing so). If the urine culture returns positive, they will be treated with a course of culture-based antibiotics and will begin Hiprex once their urine results confirm a negative culture.

Based on our preliminary data on seven women followed for one year, the levels in urine (ratioed to urinary creatinine to account for urine dilution) remain fairly stable over time.

Therefore, we don't need to follow women on Hiprex as closely as we intended to at the start of this project. Now we suggest that patients return to clinic at 3 months, 6 months, and 12 months after the onset of their Hiprex treatment to provide urine samples. During these follow-up visits, patients will also fill out a standardized, validated questionnaire regarding UTI symptoms. Data concerning common Hiprex side-effects and compliance with self-administration of Hiprex will also be collected. Hiprex will be stopped when clinically indicated based on the onset of such side-effects. Urine acidity and concentration of methenamine and formaldehyde will be analyzed in these urine samples. Hiprex dosage will be increased if concentration of formaldehyde is not above the threshold for bacteriostatic effects.

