## 14. Biostatistics:

Since this is a pilot study, our goal is to enroll 100 patients with RUTIs willing to be closely monitored for 1 year on Hiprex once the appropriate dosing has been confirmed. The acquired data will inform power calculations for a future randomized control trial.

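### Close monitoring is the stated protection for women new to Hiprex, but the first scheduled side-effect query is at month 3 and none is tied to a dose increase

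*Combined protocol and SAP*

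**What the plan says.** - **Section 10 (Potential Risks), item b** names side effects as the risk for women not already taking Hiprex, and adds that "patients will be monitored very closely after the start on Hiprex therapy". No frequency is attached.
- **Section 14 (Biostatistics)** describes the 100 women to be enrolled as "willing to be closely monitored for 1 year on Hiprex once the appropriate dosing has been confirmed".
- **Section 3, Part 2** gives the reason for fewer visits: "Based on our preliminary data on seven women followed for one year, the levels in urine", adjusted for creatinine, stayed fairly stable. It concludes that "we don't need to follow women on Hiprex as closely as we intended to at the start of this project" and proposes that "patients return to clinic at 3 months, 6 months, and 12 months after the onset of their Hiprex treatment".
- **Section 4, Follow-up** repeats the month 3, 6 and 12 schedule, says that it coincides with standard-of-care visits, and has women asked at each visit about symptoms since the previous one. If urinary concentrations are inadequate, "the dosage might be increased to 1.5 PO BID" (no unit is given). Section 3, Part 2 words the increase as something that will happen.
- **Section 11 (Subject Safety and Data Monitoring)** provides for warnings, for symptom questions at each follow-up visit, and for stopping when clinically indicated.
- **Section 4, Initial visit** advises women to come back early if they have UTI symptoms or possible side effects.
- **Section 3, Secondary outcomes** includes the frequency and severity of adverse effects that lead to interruption, dose adjustment or discontinuation.

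**The concern.** The risk section gives the impression of extra vigilance in the weeks after starting. The schedule shows none: active questions come at routine visit frequency, and the plan itself says that follow-up has been relaxed. The reason for relaxing it bears on how often urine needs to be sampled. It does not bear on how often women need to be asked how they feel. Section 2 lists "the effectiveness and safety of Hiprex in geriatric patients as well as those with comorbidities" among the gaps in knowledge, and women up to age 85 are eligible.

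Two things are at stake. Participants, and whoever approves the study, may rely on a safeguard that is less than its description. The adverse-effect outcome, which belongs to a pilot meant to inform a later randomized trial, also rests on self-initiated returns and on recall over several months. Section 2 calls the known effects typically self-limited, so some will have resolved before anyone asks.

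**Working it through.** The plan gives no figure on this point to reproduce. The check reads the schedule and takes differences.

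**Inputs.** Start of Hiprex = month 0. Scheduled queries = months 3, 6 and 12 (Section 3, Part 2; Section 4, Follow-up; Section 11). No telephone call, symptom diary or interim contact for side effects is described.

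**Interval before each scheduled query** (also the recall period):

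- Month 3: 3 − 0 = 3 months
- Month 6: 6 − 3 = 3 months
- Month 12: 12 − 6 = 6 months

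**Time from a dose increase to the next scheduled query**, for an increase made on the results of a given visit:

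| Visit prompting the increase | Next query | Gap |
|---|---|---|
| Month 3 | Month 6 | 6 − 3 = 3 months |
| Month 6 | Month 12 | 12 − 6 = 6 months |
| Month 12 | none | no query |

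The true gaps are slightly shorter, because the dose changes only once the assay results are back. The turnaround time is not stated. These gaps apply to every participant whose dose is increased, not only to new starters. The documents do not say what share of women is expected to need an increase.

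**Claim against evidence.** Section 10 speaks of closeness after the start. Section 3, Part 2 speaks of less closeness than first intended, and supports this with urinary levels in seven women. It reports nothing on side effects in those seven, so the reduction in visits has no tolerability basis in the text.

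**Effect on the outcome.** An interruption can be the woman's own decision. If she pauses the tablets in the first month and resumes, the study learns of it only if she returns early or remembers it at month 3. No section asks for the onset date or the dose in use to be recorded with a side effect.

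**The case against.** The strongest reply is that the plan does contain safeguards: warnings, advice to return early, questions at every visit and stopping when clinically indicated. Women with recurrent infections are also likely to attend between visits for symptoms. The drug is described as free of serious or lasting effects in literature going back to the 1960s. The wording about closeness has no defined frequency, and the remark about following women less closely is relative to an earlier plan. All of this is fair and limits the point. It does not make routine visit frequency into close monitoring after the start, because the provision between visits depends on the patient.

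The documents do not support several stronger readings that a reader might infer:

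- *That new starters have no protection.* Section 11 and the Initial visit text in Section 4 show otherwise. Months 6 to 12 lack scheduled contact, not all contact.
- *That side effects cannot be assigned to the original or the increased dose.* Increases follow visit samples and each query looks back to the previous visit, so the recall period roughly matches the dose period. The exceptions are the assay turnaround and any time after month 12.
- *That the seven women set a numerical bound on side-effect rates.* No side-effect data are given for them, so any such bound would be hypothetical.
- *That the increased dose exceeds nearly all earlier experience in Table 1.* This needs a unit for the increased dose, which Section 4 does not give.
- *That Section 14 makes the same safety promise as Section 10.* It describes what enrolled women are willing to accept.

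It can also be said that the secondary outcome counts only effects that lead to action, and these are easier to date than mild ones. That reduces the loss, but it does not cover pauses that a woman makes herself.

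**Conclusion.** The point holds as a conflict between the stated protection and the schedule, together with a gap in how side effects are ascertained. The first scheduled query comes 3 months after the start. After a dose increase it comes about 3 or 6 months later, or not at all if the increase follows the month-12 results.

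This rests on three assumptions: visits take place on schedule; side effects are actively asked about only where the documents say so; and the dose provision applies to every follow-up visit, including the last, as written. If no increase is ever made on month-12 results, the case with no query disappears and the rest stands.

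The consequence is moderate. The primary outcome is not directly affected. The risk statement is inaccurate as it stands, and the adverse-effect outcome is weaker than it needs to be. The correction is cheap and should be made.

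**What to change.** Reconcile Sections 10 and 14 with Section 3 (Part 2), Section 4 (Follow-up) and Section 11, in one of two ways:

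1. Keep the month 3, 6 and 12 visits and add a short scripted symptom query, by phone or portal message from existing staff. Make one between the start of Hiprex and month 3, and one after any dose change, including a change made on month-12 results.
2. Remove the wording about close monitoring and tell participants the actual schedule, including that they must report side effects between visits themselves.

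In either case, state how side effects are ascertained between visits, and record the onset date and the dose in use with each one.

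The cost is a wording amendment and two data fields. Under the first option there is also one early contact per woman (at most 100 for the planned enrollment) and one more per dose change. No clinic visits or laboratory tests are added. No dose or clinical rule is proposed here.
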